### 2.1.1 General definitions

The investigational treatment is 0.5 mg ranibizumab 10 mg/ml solution for injection, taken by patients in two different regimes: PRN or DI.

In this study, PRN is defined as the regime where after initial monthly therapy until maximum BCVA and no signs or no further improvement of disease activity, patients are monitored every month and retreated if any signs of disease activity occur.

DI is defined as the regime where the investigator treats patients at own discretion after initial monthly treatment until maximum BCVA and no signs or no further change of disease activity.

The study treatment period will be defined as starting from baseline (visit 2), which is the date of first administration of study treatment, until the last treatment (laser photocoagulation and/or ranibizumab) prior to the patient's month 12 (follow-up) visit, which is called the date of last administration of study treatment.

There are two separate treatment phases within the study period:

- an initial treatment phase

This is the period from first administration of study treatment in the study eye until the first NO treatment given based on the Ranibizumab dose administration electronic Case Report/Record Form (eCRF) when the reason for NO treatment given is one of the following three stability criteria:

- No disease activity (BCVA maximum, CRT minimum and no further signs of activity in morphologic parameters)
- Disease activity stable with maximum BCVA (no further improvement of other morphologic parameters)
- BCVA and disease activity stable (no further improvement of BCVA and other morphologic parameters).

Note: If the reason for NO treatment given was either:

- Adverse event
- Disease activity present but patient refused additional treatment

the patient will continue to remain in the initial treatment phase until the reason for NO treatment given is one of the aforementioned three stability criteria.

- a maintenance phase

This is the period from after the end of the initial treatment phase (first NO treatment given based on the Ranibizumab dose administration eCRF) until End of Study (EoS) visit.

The study day for a baseline or post-baseline scheduled or unscheduled visit is defined as

- Study day = (Date of visit) - (Date of baseline visit) + 1

- Disease activity stable with maximum BCVA (no further improvement of other morphologic parameters)
- BCVA and disease activity stable (no further improvement of BCVA and other morphologic parameters).

It will be categorized as follows:

1. No presence of fluid and BCVA stable and retinal thickness stable
2. No presence of fluid and BCVA stable and retinal thickness not stable
3. No presence of fluid and BCVA not stable and retinal thickness stable
4. No presence of fluid and BCVA not stable and retinal thickness not stable
5. Presence of fluid and BCVA stable and retinal thickness stable
6. Presence of fluid and BCVA stable and retinal thickness not stable
7. Presence of fluid and BCVA not stable and retinal thickness stable
8. Presence of fluid and BCVA not stable and retinal thickness not stable

Patients treated not in line with the stability compliance assessment will be deemed as those who according to the definition of the study compliance assessment did not meet the stability criteria but still had a NO treatment given record on the Ranibizumab dose administration eCRF when the reason for NO treatment given is one of the three stability criteria at the same visit. Otherwise they will be regarded as treated in line with the stability compliance assessment.

The stability compliance assessment will be further categorized as:

- Full stability (Yes, No)
  - Yes refers to “No presence of fluid and BCVA stable and retinal thickness stable” (criterion 1 mentioned above)
  - No refers to any of the other categories (criteria 2 to 8 mentioned above)
- Overall full stability (Yes, No)
  - Yes refers to when for each occurrence of NO treatment given due to one of the aforementioned three stability criteria for a patient the stability compliance assessment is always “No presence of fluid and BCVA stable and retinal thickness stable” (criterion 1 mentioned above)
  - No refers to when for each occurrence of NO treatment given due to one of the aforementioned three stability criteria for a patient at least once the stability

compliance assessment is not “No presence of fluid and BCVA stable and retinal thickness stable” (criterion 1 mentioned above)

The following OCT variables: CSRT, FCP thickness will be adjusted based on the OCT device used according to the correction factors outlined in [Table 2-1](#).

**Table 2-1 OCT correction factors**

Variables	OCT device	Correction factor
CSRT (µm)	Heidelberg Spectralis	No correction required
	Cirrus Zeiss*	Add 56,29 µm to unadjusted value
	Topcon	Add 121,72 µm to unadjusted value
	Other **	No correction required
	NA **	No correction required
FCP thickness (µm)	Heidelberg Spectralis	No correction required
	Cirrus Zeiss*	Add 28,3 µm to unadjusted value
	Topcon	No correction required
	Other **	No correction required
	NA **	No correction required

\* The Cirrus Zeiss OCT device refers to Cirrus Zeiss Macular Cube 512 x 128 x 1024.

\*\* A correction factor is not applicable in this case.

## 2.2 Analysis sets

The **Randomized Set (RS)** will consist of all patients who were randomized to one of the treatment arms and who received at least one application of study treatment.

The **Full Analysis Set (FAS)** will consist of all patients as randomized who received at least one application of study treatment and have at least one post-baseline assessment for the primary endpoint (BCVA). Following the intent-to-treat principle, patients will be analyzed according to the treatment assigned. No data will be excluded from the FAS analyses because of PDs.

The **Per Protocol Set (PPS)** will consist of all patients in the FAS who received study treatment as randomized and completed the treatment phase of the trial without major PDs.

Criteria that are assumed to impact the PPS will be defined in the data review plan (DRP), data handling plan (DHP), and Blind Data Review Meeting (BDRM) before DBL.

The **Safety Set** will consist of all patients from the RS who had at least one post-baseline safety assessment. Patients will be analyzed according to treatment received. The statement that a patient had no AEs also constitutes a safety assessment.

For rules of exclusion criteria of analysis sets refer to [Appendix 5.3](#).

**Table 2-2 Analysis data sets for specific outputs**

	All screened patients	RS	FAS	PPS	Safety Set
Screening failures	X				
Demographics and baseline characteristics			X		
Analysis sets		X			
Patient disposition	X	X			
Number of patients by visit		X			
Protocol deviations		X			
Medical history			X		
Concomitant medication					X
Primary and key secondary efficacy variables			X	X	
Other efficacy analyses			X		
Patient reported outcomes			X		
Safety analyses					X
Exposure					X
Subgroup analyses		X			
Non-inferiority analyses			X	X	

The number and percentage of patients in each analysis set will be summarized based on the RS.

### 2.2.1 Subgroup of interest

Gender subgroup analysis will be done for the primary objective.

For patients with [REDACTED], for patients that needed additional panretinal photocoagulation (PRP) treatment and for patients experiencing an incident leading to vitrectomy (see [Section 2.1.1](#) for definition of the subgroups of interest), separate subgroup analysis will be presented using the endpoints:

- BCVA changes in ETDRS letters from baseline to month 12
- Number of visits and treatments
- Progression/ regression of neovascularization from baseline to month 12 (i.e. change in PDR in the study eye from baseline to month 12)
- Changes in CSRT from baseline to month 12 at each visit

Patients with missing baseline values used to define the subgroups will be presented in a category “unknown” in the respective subgroup analyses.

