6. Structural damage within 0.5 disc diameter of the center of the macula in the study eye likely to preclude improvement in visual acuity following the resolution of macular edema, including atrophy of the retinal pigment epithelium, subretinal fibrosis, laser scar(s).
7. Patients with both, a BCVA score of > 73 letters and a central subfield thickness (CSFT) of < 300 µm in the study eye.
8. Uncontrolled glaucoma in either eye at screening (IOP > 24 mmHg on medication or according to investigator's judgment).
9. Neovascularization of the iris in either eye.
10. Vitreous hemorrhage impairing the adequate diagnosis of DME in the study eye
11. Evidence of clinically relevant vitreofoveal adhesion in the opinion of the investigator, vitreofoveal traction with foveal involvement or epiretinal membrane with foveal involvement in the study eye that is likely to prevent improvement of BCVA loss due to DME.
12. Proliferative vitreoretinopathy in study eye
13. History of retinal detachment, retinal tear or macular hole in the study eye.
14. Neovascularization covering an area of \geq 2 disc areas within the macula (defined as area with 6mm diameter centered on the fovea), originating either from neovascularization of the disc or multiple neovascularization's elsewhere in study eye
15. Patients who are monocular or have a BCVA score in the non-study eye (fellow eye) < 24 letters (approximate Snellen equivalent of 20/320) at Visit 1.

Prior and planned Ocular treatments

16. Any intraocular surgery in the study eye within 4 months prior to randomization.
17. Vitrectomy/vitreoretinal surgery
 - a. In the medical history or planned for study eye
 - b. planned vitrectomy or vitrectomy in last 3 months in fellow eye
18. Planned medical or surgical intervention during the 12-months study period likely to interfere with study schedule or outcomes.

19. Panretinal laser or focal/grid laser photocoagulation in the study eye within 3 months prior to randomization unless sufficient documentation of laser photocoagulation in that period of time is available.
20. Treatment with anti-angiogenic drugs (pegaptanib sodium, anecortave acetate, bevacizumab, ranibizumab, VEGF-Trap, etc.)
 - within 3 months prior to randomization for study eye
 - within 1 month prior randomization for fellow eye.
21. Use of other investigational drugs at the time of enrollment, or within 3 months or 5 half-lives from enrollment, whichever is longer.

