5.1.2 Additional study treatment

Focal/grid laser can be applied additionally in both arms but earliest at month 3.

Patients with indication for PRP (e.g. PDR, large non-perfusion areas, severe non-proliferative diabetic retinopathy) will be treated with additional panretinal photocoagulation (PRP) at baseline or at least within 3 months after randomization in both arms.

Macular ischemia should not be treated with PRP according to already mentioned guidelines.

For more details please refer to chapter [5.5.3.2 Handling of other study treatment](#).

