8.5 Adjudication Committee

Not required.

9 Data analysis

All analyses will be performed by Novartis personnel or a designated CRO.

Descriptive statistics include n, mean, standard deviation, median and ranges for continuous variables and frequencies and percentages for categorical variables and will be provided by treatment arm unless otherwise specified.

As baseline value the last assessment collected prior to start of treatment will be considered (i.e. data from screening or baseline).

Further technical details will appear in the Statistical Analysis Plan, which will be finalized prior to database lock.

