9.4.2 Statistical model, hypothesis, and method of analysis

The primary objective of this trial is to demonstrate, that the ranibizumab treatment at the discretion of the investigator (DI) is non-inferior to ranibizumab PRN treatment with respect to the mean average BCVA change from baseline to month 12.

The following hypothesis will be tested at a one-sided 0.025 level.

Non-inferiority with respect to BCVA:

$H_0: \mu_{DI} - \mu_{PRN} \leq -\Delta$ versus $HA: \mu_{DI} - \mu_{PRN} > -\Delta$

where μ_{DI} and μ_{PRN} are the unknown mean average changes from baseline in BCVA to month 12 in the DI regimen and the PRN regimen, respectively. Δ is the non-inferiority margin and is pre-defined to be 4 letters (see section 3.2 for the justification of the margin).

The hypothesis testing with respect to non-inferiority of BCVA will be carried out using an analysis of covariance model including treatment group and center as factor and baseline BCVA as continuous covariate. For the treatment contrast, the point-estimate will be given with its (two-sided, 95%-) confidence interval and the p-value for the (unshifted) null hypothesis $\mu_{DI} - \mu_{PRN} = 0$. The one-sided non-inferiority-p-value for the shifted hypothesis $\mu_{DI} - \mu_{PRN} \leq -\Delta$ will be calculated additionally. Non-inferiority will be claimed, if the lower limit of the confidence interval does not exceed $-\Delta$. (Please notice that the lower limit of a 2-sided, 95% confidence interval is identical to the lower limit of a 1-sided, 90% confidence interval which is usually used to assess non-inferiority).

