## 3 Sample size calculation

A sample size of 133 patients per treatment arm will have 90% power to establish non-inferiority at a margin of 4 letters for the 0.5 mg ranibizumab “at investigators discretion” dosing regimens in comparison to 0.5 mg ranibizumab PRN in the mean average change in BCVA based on a one-sided 0.025 significance level, assuming a treatment difference of 0 letters, a SD of 10 letters and an underlying normal distribution for an unstratified t-Test (nQuery Advisor 7.0).

The Phase III study (RESTORE) results in the FAS suggest a mean average change in BCVA of 6 letters with a SD of about 7-8 letters for ranibizumab. To account for some more variability related to the re-treatment concepts and subgroup treated with additional PRP laser in this study as compared to RESTORE, a SD of 10 letters is assumed. To account for some drop outs 150 patients will be randomized per treatment arm.

As outlined in the study protocol, section “Summary of protocol amendments” (study protocol version no.1 including Amendment 1); further recruitment of patients into this study was revised and reduced. New and relevant scientific evidence regarding treatment patterns with ranibizumab was published which did not justify continuing the trial with newly included

patients. Therefore recruitment was terminated at the time when 135 patients were enrolled into the study, resulting in a reduced sample size present for analysis.

As a consequence results are to be interpreted in a purely descriptive manner. With an estimate of about 120-150 patients to be enrolled by end of recruitment the expected power would be about 55-60% and will be evaluated accordingly.

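### By-arm outcome tables in the vitrectomy subgroup, and in the PRP subgroup so far as it rests on PRP after randomisation, may compare differently selected patients.

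*SAP*

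**What the plan says.** SAP 2.2.1 announces separate subgroup analyses "for patients that needed additional panretinal photocoagulation (PRP) treatment and for patients experiencing an incident leading to vitrectomy". The endpoints are BCVA change to month 12, number of visits and treatments, progression or regression of neovascularisation, and CSRT change. SAP 2.6.4 adds descriptive statistics of the primary outcome for the same two groups. SAP 2.2.1 refers to 2.1.1 for the definitions, which the released text of 2.1.1 does not show. It also provides an unknown category for patients whose baseline values needed for the definition are missing.

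Other parts of the documents bear on who can enter these groups:

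- **Vitrectomy.** Protocol 4.2, criterion 17a, excludes vitrectomy or vitreoretinal surgery "In the medical history or planned for study eye". Protocol Table 5-1 requires study treatment to stop after a study-eye vitrectomy.
- **PRP.** Protocol 5.1.2 has patients with an indication (for example PDR, large non-perfusion areas or severe NPDR) treated "at baseline or at least within 3 months after randomization in both arms". Protocol Appendix 2 foresees PRP re-treatment, and SAP 2.5.1.2 counts laser treatments to month 12.
- **Monitoring.** Protocol 5.5.3.3.1 starts both arms on the same monthly injections. After that, PRN patients are seen monthly and DI patients at least every 3 months.
- **Masking.** Only the VA assessor and the reading centres are masked; Protocol 3.2 leaves patients and physicians unmasked.
- **Display.** The opening of Protocol section 9 says that descriptive statistics "will be provided by treatment arm unless otherwise specified".

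**The concern.** Randomisation makes the arms comparable at entry. It does not make them comparable within a group that patients join later, if the randomised regimen can affect who joins. Here it could: an unmasked physician who sees a patient monthly may find a PRP indication or a complication earlier, or in a milder state, than one who sees the patient every 3 months. If so, the PRN subgroup would contain milder cases and DI would look worse with no effect on vision. If closer follow-up prevented or delayed such events, the selection could run the other way.

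The Protocol gives readers reason to look at these tables. Section 1.1 keeps patients with PDR and retinal ischaemia in the trial to reflect routine care, and section 1.2 expects subgroups to add knowledge about efficacy. At stake is a misleading side-by-side display of DI and PRN in patients with advanced retinopathy. The main result is not at stake.

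**Working it through.** **1. The plan's own figure.** The documents give no figure for either subgroup. The one documented input used below is the SD, so I checked that the sample size follows from it. Inputs: "A sample size of 133 patients per treatment arm will have 90% power to establish non-inferiority at a margin of 4 letters", "assuming a treatment difference of 0 letters", "a SD of 10 letters and an underlying normal distribution for an unstratified t-Test" (SAP 3), and one-sided alpha 0.025 (Protocol 9.4.2).

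n per arm = 2 × (1.960 + 1.282)² × 10² / 4² = 131.3, so 132 by the normal approximation. The exact t-test needs 133 (power 90.1%). The stated 133 reproduces.

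**2. When each group is formed.**

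- Vitrectomy: criterion 17a removes study eyes with past or planned vitrectomy, and the SAP label names an incident that a patient experiences. Membership therefore comes after randomisation.
- PRP: the indication can be present at entry and PRP can be given at baseline, so part of the group may be fixed by baseline disease. The rest may be treated in the following 3 months or, since nothing rules it out, later. The sample-size text in SAP 3 speaks of a subgroup treated with additional PRP laser, which favours reading the group as treatment received. The unknown category for missing baseline values points the other way. The released text does not settle this.

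**3. What a spurious difference requires.** Entry must depend on arm, and entry must also be related to outcome. The documents make the first possible (unmasked physicians, unequal monitoring) but do not show that it happens.

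**4. Illustrative size.** Assume no treatment effect, so BCVA change has mean 6 letters (the RESTORE figure in SAP 3) and SD 10 in both arms. A latent severity, standard normal, has correlation ρ with a worse BCVA change. A patient enters when severity exceeds an arm-specific threshold c, where p is the entry share. Then

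subgroup mean = 6 − 10 × ρ × φ(c)/p

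DI − PRN = −10 × ρ × [φ(c)/p in DI − φ(c)/p in PRN]

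The values of φ(c)/p are 2.268 (3%), 1.985 (6%), 1.755 (10%), 1.554 (15%), 1.400 (20%) and 1.271 (25%). The entry shares and ρ are assumptions; the documents give neither.

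| Subgroup, entry DI vs PRN | Difference in φ(c)/p | ρ = 0.3 | ρ = 0.5 |
|---|---|---|---|
| PRP, 15% vs 25% | 0.283 | −0.85 | −1.42 |
| PRP, 10% vs 20% | 0.355 | −1.07 | −1.78 |
| Vitrectomy, 3% vs 6% | 0.283 | −0.85 | −1.41 |
| Equal shares, same entry rule | 0 | 0 | 0 |

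Swapping the shares reverses the sign. With ρ = 0 every entry is 0. Simulation with 2,000,000 patients per arm at ρ = 0.5 gave −1.46 (15% vs 25%), +1.40 (25% vs 15%) and 0.00 (20% vs 20%).

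**5. Against sampling error.** With 135 patients (SAP 1.1) there are about 67.5 per arm. A 20% share is 13.5 patients per arm; 3% and 6% are about 2 and 4. The 95% half-width for a difference of two means with k per arm is t(0.975; 2k − 2) × 10 × √(2/k):

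- k = 13: 8.1 letters
- k = 4: 17.3 letters
- k = 2: 43.0 letters

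The selection difference of about 0.9 to 1.8 letters is well below all of these.

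**The case against.** The strongest case against has four parts.

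- **The PRP definition cannot be seen.** The group may already be set by a baseline indication, which would make it sound. Much of the 3-month PRP window also overlaps the initial monthly phase common to both arms, and SAP Table 5-4 lists PRP timing as a reportable deviation (O17). This stands, and it limits the PRP half to PRP given or needed after randomisation.
- **The vitrectomy label names no eye.** Criterion 17b excludes only planned or recent vitrectomy in the fellow eye, and a study-eye history entered in error (E15a) is only reportable. This is correct, but such cases would be exceptions, efficacy is evaluated in the study eye only, and the label describes an incident rather than a history.
- **No arm comparison is stated.** No test or interval between arms is specified for these two subgroups, and the whole analysis is declared descriptive. This stands as a limit on the consequence. By-arm display is still the Protocol default. SAP 2.6.4 departs from that default explicitly for its stability-compliance summary of the primary outcome, which is shown for the total, and sets no such limit for these groups.
- **Part of the remedy is already planned.** SAP 2.5.1.2 tabulates laser treatment by type and arm, and SAP 2.4.1 tabulates treatment discontinuation with reasons. This lowers the cost of the fix.

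A reader might infer that DI and PRN patients in these subgroups are certainly selected differently, or that the PRP group is post-randomisation whatever its definition. The documents support neither. They show a route from arm to membership, but no evidence that it operates.

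**Conclusion.** The point holds as a minor one. The vitrectomy subgroup is formed after randomisation. The PRP subgroup is too, to the extent that it rests on PRP given or needed on study. Because the trial is unmasked to physicians and its arms differ in monitoring frequency, by-arm figures inside these groups are not protected by randomisation and may mislead.

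The size and direction are unknown. Apart from the SD of 10, every input that drives the 0.9 to 1.8 letters is an assumption (the mean of 6 cancels). The figure shows what selection alone could do and is not an estimate for this trial. Noise in groups this small would exceed it. The primary FAS comparison does not use these subgroups and is unaffected.

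**What to change.** Change SAP 2.2.1 and 2.6.4 as follows.

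1. Define the PRP subgroup shown by arm from baseline data: a reading-centre DRS grade of severe NPDR or PDR, capillary non-perfusion (both in SAP 2.4.3), or a PRP indication if one is recorded at baseline. State where eyes graded at baseline as post-PRP and not gradable belong.
2. Report PRP given on study, and vitrectomy, as outcomes by arm (n, %).
3. Show BCVA, CSRT, neovascularisation and visit figures of patients with on-study PRP or vitrectomy for the total only, following the stability-compliance precedent in SAP 2.6.4. If they are kept by arm, add a statement that the arms are not comparable within the group.

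Under a baseline definition, entry cannot depend on arm, so the expected selection difference is zero. The cost is SAP wording and table shells; the reading-centre grades are already collected. The drawback is that the baseline group will not match exactly the patients who received PRP.
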